This preliminary investigation is currently being carried out by [name] of the Johns Hopkins School of Medicine. In brief, 20 healthy adult volunteers will be recruited from previous studies and advertisements. Participants will be screened after consent based on whether they are able to comply with the dietary restrictions and medication exclusions. They will be asked to refrain from consuming cruciferous vegetables and condiments (e.g., mustard, horseradish, wasabi) that might contain glucosinolates or isothiocyanates for 3 days before and during the study. Participants will fast overnight and the following morning. They will then take 7 Avmacol® tablets orally; each tablet will contain 15 mg of glucoraphanin for an expected sulforaphane dose that should average 100-150 µmol. Participants will provide a pre-dosing urine sample, and the entire urine excreted during the first 8 hours and for the following 16 hours, in segregated collections. Total dithiocarbamate excretion in each urine sample (three per participant) and urine creatinine concentrations will be determined. Dithiocarbamates (DTC) are the ultimate metabolites of sulforaphane excreted in the urine, and are readily measured by techniques developed by the Cullman Chemoprotection Center (Ye et al. 2002). It is expected that the conversion of the oral dose to the excreted DTC will be about 40%, but any mean conversion of >10% (the mean bioavailability without added myrosinase) will be considered acceptable. Preliminary results from this study are that conversion is at least 35% (personal communication, [name], March 9, 2016).

Aims

The primary aim of the study is:

1. To evaluate the safety and efficacy of a sulforaphane compound for individuals with schizophrenia who have residual psychotic symptoms of at least moderate severity in a double blind trial. The primary outcome will be the severity of psychiatric symptoms as measured by the Positive and Negative Syndrome Scale (PANSS) (Kay, Fiszbein, & Opler 1987). We will also measure cognitive functioning with the MATRICS Consensus Cognitive Battery (MCCB) (Nuechterlein et al. 2008).

Secondary aims of the study are:

- 2. To study the effect of the sulforaphane compound in lowering several biomarkers of inflammation including C-Reactive Protein (CRP), heat shock protein 90, and other markers of inflammation and cell damage.

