- 3. To investigate the association between the efficacy of sulforaphane therapy and initial and follow-up levels of these markers.

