5. STUDY DESIGN AND PROCEDURES

Study Overview

Over a two year period, we will randomize N=64 participants who have residual psychotic symptoms which are of at least moderate severity. Based on our experience performing similar clinical trials, we anticipate that we will evaluate up to 100 participants in order to randomize 64. We expect a drop-out rate of 15% after randomization. The trial will begin with a 2 week singleblind placebo run-in phase followed by a 16 week double-blind phase. During the placebo run-in phase, participants will receive placebo 6 tablets once per day. During the double-blind phase, participants will receive either the sulforaphane tablet 6 tablets once per day (equivalent to ~100 umol of sulforaphane) or the placebo 6 tablets once per day. The primary outcome that will be assessed is the severity of psychiatric symptoms as measured by the Positive and Negative Syndrome Scale (PANSS) (Kay et al. 1987). We will also measure cognitive functioning with the MATRICS Consensus Cognitive Battery (MCCB) (Nuechterlein et al. 2008). In addition, we will study the effect of the sulforaphane compound in lowering several biomarkers of inflammation including C-Reactive Protein (CRP), heat shock protein 90, and other markers of inflammation and cell damage. We will also investigate the association between the efficacy of sulforaphane therapy and initial and follow-up levels of these markers. For a detailed list of procedures and assessments at each study visit, see the Schedule of Assessments.

Study Compound

The active study compound and identical-appearing placebo will be prepared and provided by Nutramax Laboratories, Edgewood, MD, USA, the company that makes Avmacol®, a commercially-available over-the-counter compound (http://www.nutramaxstore.com/avmacolreg-60-tablets-p430.aspx). The active ingredient in Avmacol® is produced naturally by extracting the biologically inactive glucosinolate, glucoraphanin, from broccoli seeds, and compressing it in tablets with active myrosinase from broccoli sprouts. The ingestion of this compound leads to the

hydrolysis of glucoraphanin and the generation of sulforaphane within the gastrointestinal (GI) tract and the subsequent systemic absorption of the sulforaphane.

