• Positive and Negative Syndrome Scale (PANSS) (Kay et al. 1987), a rater-based scale used to assess and measure the severity of psychiatric symptoms over the past one week (unless previously obtained within the last one week)

The screening visit will take approximately two hours to complete and may be divided into separate sessions to minimize participant fatigue.

Research Laboratory Measures

Samples for these measures will be obtained at visit 2 (week 0), the start of the placebo run-in phase, and other time points as noted below.

- Blood sample (approximately 20 ml) to measure levels of immune markers and antibodies to infectious agents including high sensitivity CRP, TNF alpha, antibodies to food antigens such as casein and gliadin (Severance et al. 2012), and antibodies to NR2 (Dickerson, Stallings, Vaughan, Origoni, Khushalani, and Yolken 2012). Of note, CRP is a non-specific marker of inflammation which is elevated in many individuals with schizophrenia and has been found to be reduced by the administration of a sulforaphane nutraceutical (Bahadoran et al. 2013). These measures will also be performed at visit 7 (week 10) and visit 11 (week 18).
- Blood sample (approximately 8 ml) used to measure levels of biomarkers of inflammation including Keap 1/Nrf2-induced markers of cytoprotection and of the heat shock response (in peripheral blood mononuclear cells), using real time PCR and protein gels (Western blots). These samples will be analyzed in the Johns Hopkins Cullman Chemoprotection

- Center of [name]. These measures will also be performed at visit 7 (week 10) and visit 11 (week 18).
- Blood sample (4-6 ml) for the measurement of the blood level of the antipsychotic medication. These measures will be performed also at visit 11 (week 18).
- Throat swab samples for study of the oropharyngeal microbiome. These measures will be performed at visit 2 (week 0), visit 7 (week 10), and visit 11 (week 18)
- Urine sample for compliance and dose potency testing. Sulforaphane-glutathione dithiocarbamate (DTC) metabolites will be measured from urine provided by participants as biomarkers of compliance. These tests will also be performed at the Johns Hopkins Cullman Chemoprotection Center. These measures will also be performed at visit 7 (week 10) and visit 11 (week 18).

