7. STATISTICAL ANALYSIS

Power calculations indicate that a sample size of N=64 has 80% power to find an effect size of d = .76 with an alpha = .05 and a two-tailed test of change between groups from screening to end of study.

Aim 1: Safety data will be analyzed using incidence density analysis, to compare rates of adverse events across groups, as well as survival analysis, to assess group differences in retention. PANSS total scores will be the primary efficacy endpoint. Repeated-measures regression models will be used to assess the main effects of group and time, plus the time by group interaction. This method is able to utilize all available data from participants with

incomplete follow-up, thus including participants who drop out of the study. (Based on our experience in previous trials with this population, we anticipate attrition of about 15% over the course of the trial.) A similar analytical approach will be used for the PANSS subscales and the MCCB outcome measures.

Aim 2: Repeated measures regression modeling will also be used to evaluate the effect of medication group, time, and their interaction on inflammatory biomarkers.

Aim 3: Treatment groups will be compared with respect to initial and follow-up levels of inflammatory biomarkers using *t*-tests. If groups are found to differ in this regard, the efficacy analyses will be repeated, adding the initial biomarker levels as covariates in the model.

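### The Aim 3 analysis does not estimate the association that Aim 3 names: no marker-by-treatment effect on PANSS is fitted, and follow-up markers enter no PANSS model

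*Combined protocol and SAP*

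**What the plan says.** The aim is stated twice. Section 2 (Aims) has "To investigate the association between the efficacy of sulforaphane therapy and initial and follow-up levels of these markers", and Section 5 (Study Overview) has "We will also investigate the association between the efficacy of sulforaphane therapy and initial and follow-up levels of these markers". The markers are those of Aim 2, which concerns "lowering several biomarkers of inflammation including C-Reactive Protein (CRP), heat shock protein 90, and other markers of inflammation and cell damage".

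The Aim 3 paragraph of Section 7 gives two steps.

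- Step 1: "Treatment groups will be compared with respect to initial and follow-up levels of inflammatory biomarkers using" *t*-tests.
- Step 2: "If groups are found to differ in this regard, the efficacy analyses will be repeated, adding the initial biomarker levels as covariates in the model".

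The efficacy analyses to be repeated are those of Aim 1: "Repeated-measures regression models will be used to assess the main effects of group and time, plus the time by group interaction". Aim 2 already covers the markers as outcomes: "Repeated measures regression modeling will also be used to evaluate the effect of medication group, time, and their interaction on inflammatory biomarkers".

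On timing, Section 5 (Research Laboratory Measures) says "Samples for these measures will be obtained at visit 2 (week 0), the start of the placebo run-in phase", with repeats at weeks 10 and 18. Randomization is at visit 3, week 2. Section 9 schedules the PANSS at every visit.

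**The concern.** An association between efficacy and a marker is a statement about three things together: treatment, marker and PANSS. It asks whether the benefit of the compound is larger or smaller in participants with a given marker level, or whether PANSS improvement goes with marker change. Neither step in Section 7 puts those three together in a way that answers the question.

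If the plan is followed exactly, the trial reports between-arm marker comparisons and perhaps a covariate-adjusted efficacy model. A stated aim would be left without an estimate, although blood is drawn three times to serve Aims 2 and 3. There is also a risk in interpretation: a between-arm marker difference, or a covariate coefficient, could be reported as if it answered Aim 3.

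**Working it through.** **1. The plan's own figure.** The only computed figure is 80% power at N=64, d=0.76, two-sided alpha 0.05. It belongs to Aim 1. With the 15% attrition in Section 7, 64 x 0.85 = 54.4, or 27.2 per arm. Normal approximation: 0.76 x sqrt(27.2/2) - 1.96 = 2.80 - 1.96 = 0.84, so power is 80.0% (78.6% by noncentral t). With 32 per arm: 0.76 x 4 - 1.96 = 1.08, or 86.0% (84.9%). The stated 80% therefore reproduces after attrition. No figure is given for Aim 3. I use 27 per arm below unless stated.

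**2. The t-tests.** They have marker level as outcome, arm as factor and no PANSS variable.

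- *Initial levels.* The sample is taken at week 0 and randomization is at week 2, so a difference between arms is chance. At an assumed 0.05 level (Section 7 states none for these tests) it occurs for 5% of markers, or 1 - 0.95^3 = 14.3% for at least one of three independent markers (number and independence assumed). In simulation the test was significant in about 4-5% of trials whether the true marker-by-treatment interaction was 0 or 0.76. It carries no information on Aim 3.
- *Follow-up levels.* A difference is an effect of treatment on the marker, which the Aim 2 model already addresses.
- Section 7 does not say which of these comparisons triggers the rerun.

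**3. What the rerun's marker coefficient measures.** With no product with treatment, and with equal arms and equal marker variance, the coefficient is the average of the two arm slopes. Assumed slopes, in SD of PANSS change per marker SD, active then placebo:

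- prognostic only: (-0.25 + -0.25)/2 = -0.25; true modification 0
- matters only on active: (-0.5 + 0)/2 = -0.25; true modification -0.5
- opposite slopes: (-0.25 + 0.25)/2 = 0; true modification -0.5

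The first two cannot be told apart, and the third disappears. If the outcome is PANSS level at the nine visits from week 2 to week 18 and the marker effect grows linearly, the coefficient is further averaged over visits: -0.25 x 0.5 = -0.125, -0.125 and 0. If the effect is full from week 4, it is -0.25 x 8/9 = -0.22, -0.22 and 0. Simulation (20,000 trials per case) agrees. Under linear growth the first two cases are each significant in about 29%, 17% and 9-10% of trials at assumed PANSS correlations of 0.4, 0.6 and 0.8.

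**4. What the rerun does to the efficacy estimate.** This depends on the outcome, and the documents allow two readings. Section 7 names PANSS total scores as the endpoint; Section 5 (Clinical Outcome Measures) names the change from week 2 to week 18.

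- *Level, with week 2 as a response.* In Y = a_t + b_t x group + c x marker, the estimate of b_t is (arm difference in mean Y at t) - c x (arm difference in mean marker). The last term is the same at every visit, so b_18 - b_2 does not depend on c when data are complete. With 32 per arm and 15% dropout, the mean absolute change in simulation is 0.001-0.003 SD and the largest 0.022, against a standard error of about 0.26.
- *Change from week 2.* The week 18 group effect moves by c x (arm difference in mean marker). With 32 per arm that difference has SD sqrt(2/32) = 0.25 and mean absolute value 0.25 x 0.80 = 0.20. For a slope of -0.25 at week 18, c is 0.25 x 4.5/8 = 0.14 in size under linear growth, or 0.25 if the effect is full from week 4. The mean shift is then 0.03 to 0.05 SD. When the initial t-test is significant, the mean absolute difference is about 0.58 and the shift 0.08 to 0.15 SD.

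Under neither reading is effect modification estimated.

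**5. Follow-up levels.** Weeks 10 and 18 appear in the t-tests and as outcomes in Aim 2. The rerun adds initial levels only.

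**6. Precision of a model that does address the aim.** Take residual SD of week 2 to 18 change = 1, marker SD = 1 and 27 per arm. The marker sum of squares in one arm is about 25.3, so the slope has standard error 1/sqrt(25.3) = 0.20 in one arm and sqrt(2/25.3) = 0.28 for the difference. With t = 2.01 on 50 df, the half-widths are 0.40 and 0.56 (0.57 in simulation). Power is about 41% for a slope difference of 0.5 and 78% for 0.8. In simulation this contrast returned 0.00, -0.50 and -0.50 for the three cases in step 3.

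**The case against.** The best defence is that the rerun does give a marker-PANSS association. That is true if it is triggered. If the repeated outcome is change from week 2, the coefficient is even an association with PANSS change. It is still pooled over the arms and uses the initial level only, so it is not an association with treatment efficacy.

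Two stronger readings are tempting and should not be made.

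- A reader might infer that the rerun can never alter the efficacy result. That holds exactly only for PANSS level as outcome, week 2 as a response and complete data. The documents also allow change as the outcome, where the week 18 effect can move modestly.
- A reader might infer that the primary result is compromised. Nothing in the Aim 3 text alters the Aim 1 model.

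It can also be said that the sizes are assumed, that a proper interaction analysis has low power, and that no decision in the protocol rests on Aim 3. All three stand. They limit the weight of the point but do not remove it, because the mismatch between aim and analysis follows from the wording alone. That the investigators could add interaction terms later is a weaker defence: with several markers, an unspecified choice invites selective reporting.

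**Conclusion.** The point holds as a mismatch between aim and method, not as a want of detail: carried out exactly as written, Section 7 leaves Aim 3 unanswered. Effect modification by initial levels is never estimated, and the follow-up half of the aim has no PANSS model at all. This rests on the text and needs no numerical assumption.

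The numbers are illustrations. They depend on assumed slopes, PANSS correlations, marker and residual variances, and in the simulations on the plan's d of 0.76 taken as the true effect; the documents give no such values for the markers. The point should be fixed, but it ranks below anything that touches the primary analysis.

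**What to change.** Remove the t-test condition and replace the Aim 3 text in Section 7.

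- **Initial levels.** For a short prespecified marker list, chosen by the investigators, fit the PANSS repeated-measures model on all available data with marker-by-treatment-by-time and all lower-order terms. Report the marker-by-treatment contrast for change from week 2 to week 18 with a 95% CI. A two-way marker-by-treatment term alone is not enough when level is the outcome: it averages over visits, so under linear growth a true -0.5 appears as about -0.25. A change-score version matches the full model only with complete data. With about 15% attrition it drops participants without week 18 data, so it belongs as a sensitivity analysis.
- **Follow-up levels.** Relate PANSS change (week 2 to 18) to marker change (week 0 to 10, and week 0 to 18), with arm and an arm-by-marker-change term. Report the slope in each arm with its CI. State that this is associational because marker change is measured after randomization, that it uses only participants with the needed follow-up data, and that the marker baseline precedes the PANSS baseline by two weeks.
- **Status.** Label Aim 3 exploratory.

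The cost is new wording and a few extra models on data already being collected. The price in interpretation is the imprecision shown in step 6, which the report should state plainly.

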8. COMPENSATION

Participants will receive \$20 for completing visit 1 (screening) and \$20 for completing visit 2 (week 0). For visits 3 to 10 (weeks 2 to 16), participants will receive \$15 for each visit. At visit 11 (week 18), the ending visit, participants will receive \$20 for completing the visit and an additional \$40 completion bonus (for a total of \$60). The maximum compensation received by a participant who completes the entire trial will be \$220.

